4.2. Overall Study Duration

The study begins when the first participant signs the study ICF. The end of the study is defined as the date of the last visit of the last participant in the study or the date that the last participant has discontinued study cream and has completed applicable safety follow-up assessments or is lost to follow-up.

Participants will participate in the study for a duration of up to approximately 60 weeks: 28 days in the screening period, 8 weeks in the CT period, 44 weeks in the LTS period, and 30 days in the safety follow-up period (see Figure 1).

A participant is considered to have completed the study if they have completed all study visits, including the safety follow-up visit.

4.3. Study Termination

The investigator retains the right to terminate study participation at any time, according to the terms specified in the study contract. The investigator is to notify the IRB/IEC of the study's completion or early termination in writing, send a copy of the notification to the sponsor or sponsor's designee, and retain 1 copy for the site study regulatory file.

The sponsor may terminate the study electively or if required by a regulatory agency. In the event of significant safety findings, the study will be terminated. If the study is terminated prematurely, the sponsor will notify the investigators, the IRBs and IECs, and the regulatory bodies of the decision and reason for termination of the study.

5. STUDY POPULATION

Deviations from eligibility criteria are not allowed because they can potentially jeopardize the scientific integrity of the study, regulatory acceptability, and/or participant safety. Therefore, adherence to the criteria as specified in the Protocol is essential. Prospective approval of Protocol deviations to recruitment and enrollment criteria, also known as Protocol waivers or exemptions, are not permitted.

5.1. Inclusion Criteria

Participants are eligible to be included in the study only if all of the following criteria apply:

- 1. Adolescents aged \geq 12 years to \leq 18 years (at the screening visit).
- 2. A diagnosis of AD as defined by the Hanifin and Rajka (1980) criteria.
- 3. Duration of AD of at least 2 years.
- 4. Total IGA score of 2 to 3 at the screening and baseline visits.
- 5. Percent BSA (excluding the scalp) with AD involvement of 3% to 20% at the screening and baseline visits.
- 6. Atopic dermatitis not adequately controlled with other topical prescription therapies or when those therapies are not advisable. See Section 8.1.5.2 for further details.
- 7. Agree to discontinue all agents used to treat AD from screening through the final follow-up visit.
- 8. Willingness to avoid pregnancy or fathering children based on the criteria below.
 - a. Male participants with reproductive potential must agree to take appropriate precautions to avoid fathering children from screening through 90 days (a spermatogenesis cycle) after the last application of ruxolitinib cream and must refrain from donating sperm during this period. Permitted methods in preventing pregnancy (see Appendix A) should be communicated to the participants and their understanding confirmed.
 - b. Female participants who are WOCBP must have a negative serum pregnancy test at screening and a negative urine pregnancy test before the first application of ruxolitinib cream on Day 1 and must agree to take appropriate precautions to avoid pregnancy from screening through 30 days (1 menstrual cycle) after the last application of ruxolitinib cream and must refrain from donating oocytes during this period. Permitted methods in preventing pregnancy (see Appendix A) should be communicated to the participants and their understanding confirmed.
 - c. A female participant not considered to be of childbearing potential as defined in Appendix A is eligible.
- 9. Ability to comprehend and willingness to sign an ICF or written informed consent of the parent(s) or legal guardian(s) and written assent from the participant when possible.
 - *Note:* Participants who become legal adults during the study will be asked for their signed consent to continue the study, and in the event of lack thereof, will be discontinued from further participation.

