1. PROTOCOL SUMMARY

Protocol Title: A Phase 3, Open-Label, One-Year Safety Study of Ruxolitinib Cream in

Adolescents (Ages ≥ 12 Years to < 18 Years) With Atopic Dermatitis

Protocol Number: INCB 18424-315

Objectives and Endpoints:

Table 1 presents the primary and secondary objectives and endpoints.

Table 1: Primary and Secondary Objectives and Endpoints

Objectives	Endpoints		
Primary			
To evaluate the long-term safety and tolerability of ruxolitinib cream in adolescents with AD.	Incidence of TEAEs, assessed by monitoring the type, frequency, and severity of AEs.		
Secondary			
To further evaluate the long-term safety and tolerability of ruxolitinib cream in adolescents with AD.	Changes in vital signs, height, weight, and laboratory data for hematology and serum chemistry.		
To characterize the PK of ruxolitinib cream in adolescents with AD.	Trough concentrations of ruxolitinib at each postbaseline visit.		

Overall Design:

Table 2 presents the key study design elements. Further study details are presented after the table.

Table 2: Key Study Design Elements

Study Phase	Phase 3
Clinical Indication	Topical short-term and noncontinuous chronic treatment of mild to moderate AD in nonimmunocompromised patients 12 to 17 years of age whose disease is not adequately controlled with topical prescription therapies or when those therapies are not advisable.
Population	Male and female participants 12 to 17 years of age with a diagnosis of AD for at least 2 years, a total IGA score of 2 or 3, and BSA involvement of 3% to 20% (excluding the scalp).
Number of Participants	Approximately 100 participants will be enrolled.
Study Design	Open-label, single-group, LTS study.
Estimated Duration of Study Participation	Participants will take part in the study for up to approximately 60 weeks: 28 days in the screening period, 8 weeks in the CT period, 44 weeks in the LTS period, and 30 days in the safety follow-up period.
Data Safety Monitoring Board/Data Monitoring Committee	No
Coordinating Principal Investigator	To be determined

Treatment Groups and Duration:

[figure not shown]
This is a Phase 3, open-label, 1-year safety study of ruxolitinib cream in approximately 100 adolescents (ages \geq 12 years to < 18 years) with AD whose disease is not adequately controlled with topical prescription therapies or when those therapies are not advisable (see study design schema in Figure 1).

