2.2.1. Scientific Rationale for Study Design

As the intent of this study is to further assess the safety of ruxolitinib 1.5% cream BID in adolescents with AD in addition to what was studied in the Phase 3 studies, INCB 18424-303 and INCB 18424-304, the study population has been based on that in the Phase 3 studies, namely adolescents aged \geq 12 to < 18 years of age with AD for at least 2 years and affecting 3% to 20% BSA (excluding the scalp) plus a total IGA score of 2 or 3.

In addition, given the recent concerns about the potential thromboembolic and cancer risks of oral JAK inhibitors that are currently approved as treatments for rheumatoid arthritis (Olumiant 2021, Xeljanz 2021), the exclusion criteria have been augmented where necessary to exclude anyone with current or a history of venous thromboembolism (DVT or PE), major adverse cardiovascular events, or malignancies.

The primary and secondary objectives and endpoints focus on further assessing the safety and tolerability of ruxolitinib 1.5% cream BID in adolescents through assessment of TEAEs, vital signs (in particular height and weight), laboratory data for hematology and serum chemistry, and PK (trough concentrations of ruxolitinib).

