4. STUDY DESIGN

4.1. Overall Design

This is a Phase 3, open-label, 1-year safety study of ruxolitinib cream in adolescents (ages ≥ 12 years to < 18 years) with AD whose disease is not adequately controlled with topical prescription therapies or when those therapies are not advisable (see study design schema in Figure 1). The study will be conducted at approximately 40 sites in North America and Europe.

Approximately 100 participants with a diagnosis of AD (as defined by the Hanifin and Rajka [1980] criteria) with a duration of disease of at least 2 years, a total IGA score of 2 or 3, and %BSA affected by AD of 3% to 20% (excluding the scalp) will be enrolled.

All participants will apply ruxolitinib cream at the FDA-approved strength (1.5%) BID using the same treatment paradigm as the INCB 18424-303 and -304 Phase 3 AD studies, namely starting with an 8-week CT period during which participants will treat all baseline AD lesions, regardless of whether or not the lesion(s) improve, followed by a 44-week LTS period during which participants will only treat active AD lesions.

Participants who complete the Week 8 assessments with no safety concerns and with %BSA affected by AD no greater than 20% will continue into the LTS period.

During the LTS period (ie, starting at the Week 8 visit), the treatment regimen will continue to be ruxolitinib 1.5% cream BID; however, participants will only treat active AD lesions. Participants will have the next study visit at Week 12, and then subsequent study visits will occur every 8 weeks until the end of the study (44 weeks total in the LTS period and 52 weeks total in the study). At those study visits, AD lesions will be evaluated by the investigator to confirm if the participant still requires continuation of therapy (total IGA score \geq 1) or can otherwise (re)enter the observation/no treatment cycle (total IGA score = 0). Refer to Section 6.1 for further details.

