## 1. INTRODUCTION

This is an open-label, 1-year safety study with an LTS period. Adolescents aged  $\geq 12$  to  $< 18$  years with AD for at least 2 years and affecting 3% to 20% BSA (excluding the scalp) plus a total IGA score of 2 or 3. The primary purpose of this study is to collect additional long-term safety data regarding the types, severity, and frequencies of TEAEs occurring in adolescents with AD who are treated with ruxolitinib 1.5% cream BID.

The purpose of this SAP is to provide details of the statistical analyses that have been outlined in the INCB 18424-315 Protocol. The scope of this plan includes the final analyses that are planned and will be executed by the Department of Biostatistics or designee and the Department of Clinical Pharmacokinetics or designee will execute the analysis of PK.

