**Table 5: Criteria for Clinically Notable Vital Sign Abnormalities for Age  $\geq 16$  to  $< 18$  Years**

Parameter	High Threshold	Low Threshold
Systolic blood pressure	$> 120$ mmHg	$< 90$ mmHg
Diastolic blood pressure	$> 85$ mmHg	$< 50$ mmHg
Pulse	$> 100$ bpm	$< 45$ bpm
Temperature	$> 38.0^{\circ}\text{C}$	$< 35.5^{\circ}\text{C}$
Respiratory rate	$> 20$ breaths/min	$< 8$ breaths/min

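### Inclusion criterion 1, as supplied, admits 18-year-olds, while the title, Table 2 and the SAP define the population as under 18.

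*Protocol*

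**What the plan says.** The eligibility rule is Protocol Section 5.1, criterion 1: "Adolescents aged \geq 12 years to \leq 18 years (at the screening visit".

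The other statements of the population exclude age 18:

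- Protocol title: "Adolescents (Ages ≥ 12 Years to < 18 Years) With Atopic Dermatitis".
- Protocol Table 2, population row: "Male and female participants 12 to 17 years of age with a diagnosis of AD for at least 2 years". The indication row of the same table has the same 12-to-17 range.
- Protocol Section 2.2.1: "namely adolescents aged \geq 12 to < 18 years of age with AD for at least 2 years".
- Protocol Section 4.1: "adolescents (ages ≥ 12 years to < 18 years) with AD whose disease is not adequately controlled".
- SAP Section 1: "Adolescents aged $\geq 12$ to $< 18$ years with AD for at least 2 years". SAP Section 3 repeats the same limits.

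The SAP's age-banded vital-sign criteria end at the same place. Table 4 covers ages 12 to under 16, and Table 5 is titled "Criteria for Clinically Notable Vital Sign Abnormalities for Age $\geq 16$ to $< 18$ Years". There is no further band.

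Protocol Section 5 does not permit deviations from, or waivers of, the eligibility criteria. The note to criterion 9 asks participants who reach legal adulthood while on study to consent for themselves. The Amendment 1 summary in Appendix C lists no change to criterion 1.

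**The concern.** Sites enrol from Section 5.1, not from the title. If the written rule is wider than the intended population, a site can enrol an 18-year-old correctly under the protocol and still put someone into the data whom the study was not designed to describe. The study is a post-marketing safety study in adolescents, with growth measures (height and weight) among its secondary endpoints. An unintended adult stratum therefore bears on what the summaries can be said to represent. The other issue is practical: the SAP has no clinically notable vital-sign criteria for a participant of that age.

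**Working it through.** **1. Is the conflict real or a reading error?** The text available for this review was machine-read from PDF, so a single ≤ could be a misread <. Two places use the same mix of symbols as criterion 1 (a converted ≥ sign for the lower limit) and still keep a strict < for the upper limit: the design paragraph of the Protocol Summary and Section 2.2.1. That argues against a systematic conversion fault. It does not exclude a fault in one line. The amendment summary offers no sign of a deliberate widening.

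**2. Follow one participant aged 18 at screening through the plan, taking criterion 1 as supplied.**

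| Step | Rule | Result |
|---|---|---|
| Eligibility | Protocol 5.1, criterion 1 | Met |
| Deviation or violation record | SAP 6.3; Listings 2.1.2 and 2.2 | None for age, because the criterion is met |
| Full analysis set | Protocol Table 11; SAP 5.3.1: applied cream at least once | Included |
| Primary TEAE tables | SAP 9.2.2; Appendix A | Included; planned subgroups are sex, race and ethnicity, not age |
| Height, weight, laboratory | SAP 9.3 and 9.4; FAS | Included |
| PK | PK-evaluable population | Included if at least one postbaseline sample |
| Clinically notable vital signs | SAP Tables 4 and 5 | No band |

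**3. Does the vital-sign gap come only from criterion 1?** The SAP does not say whether age is taken at screening or at each assessment. If it is taken at assessment, the gap exists under either eligibility limit. Week 52 is 52 × 7 = 364 days of treatment, and the follow-up visit is at least 30 days later: 364 + 30 = 394 days. With Week 52 at its earliest (7 days early), it is 387 days. Both exceed 366. So every participant aged 17 on Day 1 who completes Week 52 and attends the separate follow-up visit is 18 by then, and vital signs are scheduled at that visit (Protocol Table 4).

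**4. Does the sample-size statement change?** Inputs from Protocol Section 10.1 are about 100 participants, a 5% underlying rate and a stated chance above 99% of seeing at least one event. The formula is P = 1 − (1 − 0.05)^n.

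- n = 100: 1 − 0.95^100 = 0.9941. The plan's figure is reproduced.
- n = 95: 0.9924.
- n = 90: 0.9901.
- n = 89: 0.9896.

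The age limit does not enter the formula. For those under 18 alone, the statement holds as long as at least 90 of 100 are under 18.

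**The case against.** The strongest reply is that everything rests on one machine-read symbol, in a text with other visible conversion damage. This stands as a reason to check the source PDF before acting. It does not remove the point, for the reason in step 1 of the working.

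A second reply is that context protects the reader. Criterion 1 speaks of adolescents, whom the title defines as under 18, and the criterion 9 note fits entry before adulthood. An upper limit of 18 can also be read as exact age, which would admit almost nobody beyond the 18th birthday. This is fair, and it limits the likely number. But a site applying completed years would admit the whole 18th year, and an eligibility rule should not depend on which reading a site chooses.

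A third reply is that a few 18-year-olds would hardly move the tables. Protocol Section 2.3 reports no meaningful difference in TEAE profile between adults and adolescents, and the demographic summary and listing would show their ages. That supports a modest remedy. It does not make the two definitions agree.

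Several stronger inferences are tempting and not supported:

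- **That the study loses its detection probability.** This needs more than 10 of 100 participants aged 18, and the documents give no age mix from which to assume that.
- **That the ban on waivers hides the problem.** Section 5 bars deviations and prospective waivers. It does not bar recording deviations. No deviation arises because the criterion is met.
- **That enrolling an 18-year-old breaches the regulatory requirement.** Protocol Section 2.2 calls this a Post-Marketing Requirement study, but the requirement's own age range is not given.
- **That correcting criterion 1 closes the vital-sign gap.** It does not if age is taken at assessment. In any case such participants remain in the descriptive vital-sign tables; what lacks criteria is the listing of clinically notable values, and the alert listing too if its normal range means these bands.

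**Conclusion.** The inconsistency holds on the text as supplied, with confidence limited by the possibility of a single misread symbol. The operative eligibility rule is wider at the top than the population stated in the title, Table 2, Protocol Sections 2.2.1 and 4.1, and the SAP. The consequence is a possible group of 18-year-olds, of unknown size and possibly empty, inside the full analysis set with no deviation flag, no AE table by age and no vital-sign band. No sample-size figure or analysis method is affected. The documents do not show that anyone aged 18 was enrolled. This should be corrected because it is an eligibility threshold and cheap to settle, not because it threatens the study's conclusions.

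**What to change.** 1. Check the symbol in the source PDF. If it is <, nothing in criterion 1 needs changing.
2. If it is ≤, reconcile criterion 1 with the other statements by making it at least 12 years and under 18 years at the screening visit. This is one symbol, in the next amendment or a clarification letter.
3. Check recorded age at screening for everyone enrolled. If nobody was 18, say so in the study report. If anyone was, report the count and show the overall TEAE summary with and without them. That is at most one additional summary table.
4. Add a sentence to SAP Section 9.4 saying whether the bands in Tables 4 and 5 use age at screening or at assessment, and which band applies to anyone aged 18. This is needed whatever the symbol proves to be. Protocol Section 8.1.5.1 collects year of birth or age, so age at later visits may be known only approximately; the choice should allow for that.

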5.2. Exclusion Criteria

Participants are excluded from the study if any of the following criteria apply:

- 1. An unstable course of AD (spontaneously improving or rapidly deteriorating) as determined by the investigator in the 4 weeks prior to baseline.
- 2. Concurrent conditions and history of other diseases:
 - a. Immunocompromised (eg, lymphoma, acquired immunodeficiency syndrome, Wiskott-Aldrich syndrome).
 - b. Chronic or acute infection requiring treatment with systemic antibiotics, antivirals, antiparasitics, antiprotozoals, or antifungals within 2 weeks before baseline.
 - c. Active acute bacterial, fungal, or viral skin infection (eg, herpes simplex, herpes zoster, chickenpox) within 1 week before baseline.
 - d. Any other concomitant skin disorder (eg, generalized erythroderma such as Netherton syndrome), pigmentation, or extensive scarring that, in the opinion of the investigator, may interfere with the evaluation of AD lesions or compromise participant safety.
 - e. Presence of AD lesions only on the hands or feet without prior history of involvement of other classic areas of involvement such as the face or the flexural folds.
 - f. Other types of eczema.
 - g. Current or history of hepatitis B or C virus infection.
- 3. Any current and/or history of serious illness or medical, physical, or psychiatric condition(s) that, in the investigator's opinion, would interfere with full participation in the study, including application of study cream and attending required study visits; pose a significant risk to the participant; or interfere with interpretation of study data. For example:
 - a. Clinically significant or uncontrolled cardiovascular disease, including unstable angina, acute myocardial infarction or stroke within 6 months from Day 1 of study cream application, New York Heart Association Class III or IV congestive heart failure, and arrhythmia requiring therapy or uncontrolled hypertension (blood pressure > 150/90 mm Hg) unless approved by the medical monitor/sponsor.
 - b. Current and/or history of malignancy in the 5 years preceding the baseline visit, except for adequately treated, nonmetastatic nonmelanoma skin cancer.
 - c. Current and/or history of arterial or venous thrombosis, including DVT and PE.
 - d. Current and/or history of active tuberculosis or current and/or history of latent tuberculosis unless adequately treated.
- 4. Any of the following clinical laboratory test results at screening:
 - a. Hemoglobin < 100 g/L (< 10 g/dL)
 - b. Liver function tests:
 - AST or ALT $> 2.5 \times ULN$
 - Total bilirubin $> 1.5 \times ULN$ with the exception of Gilbert disease.
 - c. Estimated glomerular filtration rate < 30 mL/min/1.73 m² (using the CKD Epidemiology Collaboration equation).
 - d. Positive serology test results for HIV antibody.
 - e. Any other clinically significant laboratory result that, in the opinion of the investigator, poses a significant risk to the participant.

- 5. Use of any of the following treatments within the indicated washout period before baseline:
 - a. 5 half-lives or 12 weeks, whichever is longer biologic agents (eg, dupilumab). For biologic agents with washout periods longer than 12 weeks (eg, rituximab), consult the medical monitor.
 - b. 4 weeks systemic corticosteroids or adrenocorticotropic hormone analogues, cyclosporine, methotrexate, azathioprine, or other systemic immunosuppressive or immunomodulating agents (eg, mycophenolate or tacrolimus).
 - c. 2 weeks immunizations with live-attenuated vaccines; sedating antihistamines, unless on long-term stable regimen (nonsedating antihistamines are permitted). *Note:* Live-attenuated vaccines are not recommended during the CT period. *Note:* COVID-19 vaccination is allowed.
 - d. 1 week use of other topical treatments for AD (other than bland emollients, eg, Aveeno® creams, ointments, sprays, soap substitutes), such as topical antiprurities (eg, doxepin cream), corticosteroids, calcineurin inhibitors, PDE4 inhibitors, coal tar (shampoo), antibiotics, or antibacterial cleansing body wash/soap.

 Note: Diluted sodium hypochlorite "bleach" baths are allowed as long as they do not exceed 2 baths per week and their frequency remains the same throughout the study.
- 6. Previously received systemic or topical JAK inhibitors (eg, ruxolitinib, tofacitinib, baricitinib, filgotinib, lestaurtinib, pacritinib).
- 7. Ultraviolet light therapy or prolonged exposure to natural or artificial sources of UV radiation (eg, sunlight or tanning booth) within 2 weeks prior to the baseline visit and/or intention to have such exposure during the study, which is thought by the investigator to potentially impact the participant's AD.
- 8. Pregnant or lactating, or considering pregnancy during the period of their study participation.
- 9. History of alcoholism or drug addiction within 1 year before screening or current alcohol or drug use that, in the opinion of the investigator, will interfere with the participant's ability to comply with the administration schedule and study assessments.
- 10. Current treatment or treatment within 30 days or 5 half-lives (whichever is longer) before baseline with another investigational medication or current enrollment in another investigational drug protocol.
- 11. Current treatment or treatment within 30 days or 5 half-lives (whichever is longer) before baseline with a strong CYP3A4 inhibitor.
- 12. Removed during Protocol Amendment 1.
- 13. Known allergy or reaction to any component of the study cream formulation.
- 14. In the opinion of the investigator unable or unlikely to comply with the administration schedule and study evaluations.
- 15. Committed to a mental health institution by virtue of an order issued either by the judicial or the administrative authorities.
- 16. Employees of the sponsor or investigator or are otherwise dependents of them.

